5.0 METHODOLOGY

5.1 Entry Criteria

5.1.1 Diagnosis/Condition for Entry into the Trial

Healthy male and female subjects (at least one of each gender) between the ages of 18 and 55 (inclusive) will be enrolled in Part I. Healthy elderly male and female subjects (at least one of each gender) between the ages of 55 and 85 years (inclusive) will be enrolled in Part II of this trial. In Part III, male and female moderate to severely impaired AD patients (MMSE score \leq 20) between the ages of 55 and 85 years (inclusive) will be enrolled in this trial.

5.1.2 Subject Inclusion Criteria

In order to be eligible for participation in this trial, the subject must:

Part I, II, and III:

1. Provide written informed consent/assent for the trial. The subject may also provide consent/assent for Future Biomedical Research. However, the subject may participate in the main trial without participating in Future Biomedical Research. For AD patients in Part III, if the investigator determines that the patient is unable to provide their own informed consent, the patient's legal representative must understand the study procedures and provide written informed assent for the patient, in accordance with local requirements.
2. Be male or non-pregnant and non-breast feeding female of 18 to 55 years (inclusive) (Part I) or 55 to 85 (inclusive) (Parts II and III) years of age at the pre-trial (screening) visit; further:
 - a. If male and has intercourse with females of childbearing potential, subject must be willing to use a condom from the first dose of study medication until 3 months post the last dose of study medication. The use of a condom is an additional safety measure to the use of a contraceptive by the subject's partner. Female partners must additionally use one of the following methods: hormonal contraception, intra-uterine device, diaphragm, cervical cap.
 - b. If female with reproductive potential: subject must demonstrate a serum β -human chorionic gonadotropin (β -hCG) level consistent with the nongravid state at the pretrial (screening) visit and agree to use (and/or have their partner use) two (2) acceptable methods of birth control beginning at the pretrial (screening) visit, throughout the trial (including washout intervals between treatment periods/panels) and until 2 weeks after the last dose of trial drug in the last treatment period. Acceptable methods of birth control are defined in Section 5.7.4.1.

c. If female of non-childbearing potential, subject/patient can be:

- i. A postmenopausal female: subject/patient is without menses for at least 1 year and has a follicle stimulating hormone (FSH) value in the postmenopausal range upon pretrial (screening) evaluation,
OR
- ii. A female who is status post hysterectomy, oophorectomy or tubal ligation.

NOTE: These procedures must be confirmed with medical records. In the absence of documentation, hysterectomy may be confirmed by pelvic exam or if necessary by ultrasound; oophorectomy may be confirmed by hormone levels, particularly FSH in the post-menopausal range, but tubal ligation subjects without records should be excluded. Information must be captured appropriately within the site's source documents.

3. Have a Body Mass Index (BMI) $\leq 35 \text{ kg/m}^2$, inclusive with height no greater than 195 cm and weight no greater than 136 kg. BMI = weight (kg)/height (m) 2 .
4. Be judged to be in good health (Part I) or be generally healthy (Parts II and III) based on medical history, physical examination, vital sign measurements and ECG performed prior to randomization. Appendix 12.5 provides a table of 12-Lead Electrocardiogram Abnormality Criteria.
5. Be judged to be in good health based on laboratory safety tests (Section 7.1.3.1) obtained at the screening visit and prior to administration of the initial dose of trial drug. Section 12.6 provides an algorithm for the assessment of out-of-range laboratory values.
6. Have a negative urinary drug screen upon inclusion Exception: Subject with positive results may participate in the trial as long as the result can be rationalized as a consequence of concurrent use of a medication as permitted per protocol (see Section 5.5).
7. Be a nonsmoker and/or has not used nicotine or nicotine-containing products (e.g., nicotine patch) for at least approximately 3 months.
8. Be willing to comply with the trial restrictions (see Section 5.7 for a complete summary of trial restrictions).

Additional Inclusion Criteria for Part II only:

9. Be willing to allow the investigator(s) to place an arterial catheter in the radial artery and is assessed via physical examination (Allen Test and/or Doppler Study) to be a good candidate for arterial catheter placement.
10. Mini Mental Status Examination (MMSE) score ≥ 27 .
11. No history of subjective memory or other cognitive complaints

12. No objective evidence of memory or cognitive impairment

Additional Inclusion Criteria for Part III only:

13. Subjects must have moderate to severe Alzheimer's disease as defined by:

- a. Mini Mental Status Examination (MMSE) score ≤ 20
- b. Meet the National Institute of Neurological and Communicative Diseases and Stroke/Alzheimer's Disease and Related Disorders Association (NINCDS-ADRDA) criteria for probable AD
- c. Meet Diagnostic and Statistical Manual of Mental Disorders, 5th Edition (DSM-V) criteria for AD
- d. Rosen-Modified Hachinski score ≤ 4
- e. MRI scan obtained at screening is consistent with a diagnosis of AD.

14. Each subject must have a clear history of cognitive and functional decline over at least one year that is either:

- a. documented in medical records, or
- b. documented by history from an informant who knows the subject well.

15. Be on a stable dose of an acetylcholinesterase inhibitor for symptomatic treatment of AD. Allowable AChEIs are donepezil and rivastigmine. Other AChEIs require prior consultation with the SPONSOR. The dose must be stable for at least the last 4 weeks before screening, and the subject must be willing to remain on the same dose for the duration of the trial. The treatment dose at screening should not be changed during the trial unless medically necessary. Additional treatments for AD that are not specified in the protocol should not be initiated during the trial. The subject and caregiver must agree that they do not plan to discontinue treatment or initiate additional AD treatments during the trial unless medically necessary. **Every effort should be made to enroll** a minimum of 3 subjects already on a stable dose of donepezil.

16. Each subject must have a reliable trial partner/caregiver (i.e., spouse, sibling, child, close friend) such that he/she is knowledgeable of the subject's condition and progress.

- a. The trial partner/caregiver must be able to understand the nature of the trial and adhere to trial requirements (e.g., visit schedules, evaluations).
- b. If appropriate, the trial partner/caregiver must be willing to accompany the subject to all visits. However, at the discretion of the investigator, the trial partner/caregiver may not be required to accompany the subject to all visits (**Note:** Trial partner/caregiver is not required to stay in-house).

- c. Trial partner/caregiver must be able to provide information to study investigator/staff via telephone contact.

5.1.3 Subject Exclusion Criteria

The subject must be excluded from participating in the trial if the subject:

Part I:

1. Is under the age of legal consent.
2. Is mentally or legally incapacitated, has significant emotional problems at the time of pretrial (screening) visit or expected during the conduct of the trial or has a history of clinically significant psychiatric disorder of the last 5 years. Subjects who have had situational depression may be enrolled in the trial at the discretion of the investigator.
3. Has a history of clinically significant endocrine, gastrointestinal, cardiovascular, hematological, hepatic, immunological, renal, respiratory, genitourinary or major neurological (including stroke and chronic seizures) abnormalities or diseases. Subjects with a history of uncomplicated kidney stones, as defined as spontaneous passage and no recurrence in the last 5 years, or childhood asthma may be enrolled in the trial at the discretion of the investigator
4. Has a history of cancer (malignancy).

Exceptions: (1) Subjects with adequately treated non-melanomatous skin carcinoma or carcinoma in situ of the cervix may participate in the trial; (2) Subjects with other malignancies which have been successfully treated ≥ 10 years prior to the pretrial (screening) visit where, in the judgment of both the investigator and treating physician, appropriate follow-up has revealed no evidence of recurrence from the time of treatment through the time of the pretrial (screening) visit (except those cancers identified at the beginning of exclusion criterion 4); or, (3) Subjects, who, in the opinion of the trial investigator, are highly unlikely to sustain a recurrence for the duration of the trial.

5. Has a history of significant multiple and/or severe allergies (e.g. food, drug, latex allergy), or has had an anaphylactic reaction or significant intolerance to prescription or non-prescription drugs or food.
6. Is positive for hepatitis B surface antigen, hepatitis C antibodies or HIV.
7. Had major surgery, donated or lost 1 unit of blood (approximately 500 mL) within 4 weeks prior to the pretrial (screening) visit.
8. Has participated in another investigational trial within 4 weeks (or 5 half-lives), whichever is greater, prior to the pretrial (screening) visit. The window will be derived from the date of the last visit in the previous trial.
9. Has QTc interval ≥ 470 msec (for males) or ≥ 480 msec (for females).

10. Is unable to refrain from or anticipates the use of any medication, including prescription and non-prescription drugs or herbal remedies beginning approximately 2 weeks (or 5 half-lives) prior to administration of the initial dose of trial drug, throughout the trial (including washout intervals between treatment periods), until the post-trial visit. There may be certain medications that are permitted, see Section 5.5.
11. Consumes greater than 3 glasses of alcoholic beverages (1 glass is approximately equivalent to: beer [354 mL/12 ounces], wine [118 mL/4 ounces], or distilled spirits [29.5 mL/1 ounce]) per day. Patients that consume 4 glasses of alcoholic beverages per day may be enrolled at the discretion of the investigator.
12. Consumes excessive amounts, defined as greater than 6 servings (1 serving is approximately equivalent to 120 mg of caffeine) of coffee, tea, cola, energy-drinks, or other caffeinated beverages per day.
13. Is currently a regular or recreational user of cannabis, any illicit drugs or has a history of drug (including alcohol) abuse within approximately 3 months.
14. Has participated in a PET study or other study involving administration of a radioactive substance or ionizing radiation within 12 months prior to the screening visit, or has undergone an extensive radiological examination within this period with a radiation burden over 10 mSv (such as a CT-scan exam or a nuclear medical examination).
15. Suffers from claustrophobia or an inability to tolerate confinement in small places and would be unable to undergo MRI or PET scanning.
16. Is any concern by the investigator regarding (1) the safe participation of the subject in the trial, (2) the ability of the subject to tolerate procedures (for example, subjects with vague low back pain syndromes or subclinical hyperactivity spectrum disorders), or (3) for any other reason the investigator considers the subject inappropriate for participation in the trial.
17. Is or has an immediate family member (e.g., spouse, parent/legal guardian, sibling or child) who is investigational site or sponsor staff directly involved with this trial.

Part II

1. Is under the age of legal consent.
2. Is mentally or legally incapacitated, has significant emotional problems at the time of pretrial (screening) visit or expected during the conduct of the trial or has a history of clinically significant psychiatric disorder of the last 5 years. Subjects who have had situational depression may be enrolled in the trial at the discretion of the investigator.
3. Has a history of clinically significant endocrine, gastrointestinal, cardiovascular, hematological, hepatic, immunological, renal, respiratory, genitourinary or major neurological (including stroke and chronic seizures) abnormalities or diseases that is not adequately controlled through a stable medication regimen. Subjects with a history of uncomplicated kidney stones, as defined as spontaneous passage and no recurrence in the last 5 years, or childhood asthma may be enrolled in the trial at the discretion of the investigator

4. Has been administered an AChEI for any purpose within the prior 3 months or anticipates a requirement for administration of an AChEI for any purpose during the course of the study investigations.
5. Has incidental findings on an MRI scan that is pathognomonic for an active disease or pathological process that requires medical intervention.
6. Has implanted or embedded metal objects, or fragments in the head or body that would present a risk during the MRI scanning procedure, or have worked with ferrous metals either as a vocation or hobby (for example, as a sheet metal worker, welder, or machinist) in such a way that might have led to unknown, indwelling metal fragments that could cause injury if they moved in response to placement in the magnetic field.
7. Has a history of cancer (malignancy).

Exceptions: (1) Subjects with adequately treated non-melanomatous skin carcinoma or carcinoma in situ of the cervix may participate in the trial; (2) Subjects with other malignancies which have been successfully treated ≥ 10 years prior to the pretrial (screening) visit where, in the judgment of both the investigator and treating physician, appropriate follow-up has revealed no evidence of recurrence from the time of treatment through the time of the pretrial (screening) visit (except those cancers identified at the beginning of exclusion criterion 4); or, (3) Subjects, who, in the opinion of the trial investigator, are highly unlikely to sustain a recurrence for the duration of the trial.

8. Has a history of significant multiple and/or severe allergies (e.g. food, drug, latex allergy), or has had an anaphylactic reaction or significant intolerance to prescription or non-prescription drugs or food. **For Part II, this includes any known allergy to lidocaine which may be used as an anesthetic for the placement of the arterial catheter.**
9. Is positive for hepatitis B surface antigen, hepatitis C antibodies or HIV.
10. Had major surgery, donated or lost 1 unit of blood (approximately 500 mL) within 4 weeks prior to the pretrial (screening) visit.
11. Has participated in another investigational trial within 4 weeks (or 5 half-lives), whichever is greater, prior to the pretrial (screening) visit. The window will be derived from the date of the last visit in the previous trial.
12. Has QTc interval ≥ 470 msec (for males) or ≥ 480 msec (for females).
13. Is unable to refrain from or anticipates the use of any prescription and non-prescription herbal remedies beginning approximately 2 weeks (or 5 half-lives) prior to administration of the initial dose of trial drug, throughout the trial (including washout intervals between treatment periods), until the post-trial visit. **Of note, subject should be excluded from Part II if he/she currently uses aspirin (ASA) or aspirin-containing medications (> 80 mg/day ASA), or non-steroidal anti-inflammatory drugs (NSAIDS), which cannot be discontinued 2 weeks prior to dosing and throughout the course of the study.** There are certain medications that are permitted, see Section 5.5.

14. Consumes greater than 3 glasses of alcoholic beverages (1 glass is approximately equivalent to: beer [354 mL/12 ounces], wine [118 mL/4 ounces], or distilled spirits [29.5 mL/1 ounce]) per day. Patients that consume 4 glasses of alcoholic beverages per day may be enrolled at the discretion of the investigator.
15. Consumes excessive amounts, defined as greater than 6 servings (1 serving is approximately equivalent to 120 mg of caffeine) of coffee, tea, cola, energy-drinks, or other caffeinated beverages per day.
16. Is currently a regular or recreational user of cannabis, any illicit drugs or has a history of drug (including alcohol) abuse within approximately 3 months.
17. Has participated in a PET study or other study involving administration of a radioactive substance or ionizing radiation within 12 months prior to the screening visit, or has undergone an extensive radiological examination within this period with a radiation burden over 10 mSv (such as a CT-scan exam or a nuclear medical examination).
18. Suffers from claustrophobia or an inability to tolerate confinement in small places and would be unable to undergo MRI or PET scanning.
19. Is any concern by the investigator regarding (1) the safe participation of the subject in the trial, (2) the ability of the subject to tolerate procedures (for example, subjects with vague low back pain syndromes or subclinical hyperactivity spectrum disorders), or (3) for any other reason the investigator considers the subject inappropriate for participation in the trial.
20. Is or has an immediate family member (e.g., spouse, parent/legal guardian, sibling or child) who is investigational site or sponsor staff directly involved with this trial.

Part III:

1. Is under the age of legal consent.
2. Is mentally or legally incapacitated, has significant emotional problems at the time of pretrial (screening) visit or expected during the conduct of the trial or has a history of clinically significant psychiatric disorder of the last 5 years (**with the exception of AD**). Subjects who have had situational depression may be enrolled in the trial at the discretion of the investigator.
3. Has a history of clinically significant endocrine, gastrointestinal, cardiovascular, hematological, hepatic, immunological, renal, respiratory, genitourinary or major neurological (including stroke and chronic seizures) abnormalities or diseases is not adequately controlled through a stable medication regimen. Subjects with a history of uncomplicated kidney stones, as defined as spontaneous passage and no recurrence in the last 5 years, or childhood asthma may be enrolled in the trial at the discretion of the investigator.

4. Has been administered galantamine for any purpose within the prior 7 days or anticipates a requirement for administration of galantamine for any purpose during the course of the study investigations.
5. Has incidental findings on an MRI scan that is pathognomonic for an active disease other than AD or pathological process that requires medical intervention.
6. Has implanted or embedded metal objects, or fragments in the head or body that would present a risk during the MRI scanning procedure, or have worked with ferrous metals either as a vocation or hobby (for example, as a sheet metal worker, welder, or machinist) in such a way that might have led to unknown, indwelling metal fragments that could cause injury if they moved in response to placement in the magnetic field.
7. Has a history (within 2 years of the prestudy/screening visit) or current evidence of any neurological or neurodegenerative disorder other than AD that is associated with transient or sustained alterations in cognition.
8. Has a history (within 2 years prior to the prestudy visit) or current evidence of a psychotic disorder, or a major depressive disorder by DSM-V criteria
9. Has a history of cancer (malignancy).

Exceptions: (1) Subjects with adequately treated non-melanomatous skin carcinoma or carcinoma in situ of the cervix may participate in the trial; (2) Subjects with other malignancies which have been successfully treated ≥ 10 years prior to the pretrial (screening) visit where, in the judgment of both the investigator and treating physician, appropriate follow-up has revealed no evidence of recurrence from the time of treatment through the time of the pretrial (screening) visit (except those cancers identified at the beginning of exclusion criterion 4); or, (3) Subjects, who, in the opinion of the trial investigator, are highly unlikely to sustain a recurrence for the duration of the trial.

10. Has a history of significant multiple and/or severe allergies (e.g. food, drug, latex allergy), or has had an anaphylactic reaction or significant intolerance to prescription or non-prescription drugs or food.
11. Is positive for hepatitis B surface antigen, hepatitis C antibodies or HIV.
12. Had major surgery, donated or lost 1 unit of blood (approximately 500 mL) within 4 weeks prior to the pretrial (screening) visit.
13. Has participated in another investigational trial within 4 weeks (or 5 half-lives), whichever is greater, prior to the pretrial (screening) visit. The window will be derived from the date of the last visit in the previous trial.
14. Has QTc interval ≥ 470 msec (for males) or ≥ 480 msec (for females).

15. Is unable to refrain from or anticipates the use of any prescription and non-prescription herbal remedies beginning approximately 2 weeks (or 5 half-lives) prior to administration of the initial dose of trial drug, throughout the trial (including washout intervals between treatment periods), until the post-trial visit. There are certain medications that are permitted, see Section 5.5.
16. Consumes greater than 3 glasses of alcoholic beverages (1 glass is approximately equivalent to: beer [354 mL/12 ounces], wine [118 mL/4 ounces], or distilled spirits [29.5 mL/1 ounce]) per day. Patients that consume 4 glasses of alcoholic beverages per day may be enrolled at the discretion of the investigator.
17. Consumes excessive amounts, defined as greater than 6 servings (1 serving is approximately equivalent to 120 mg of caffeine) of coffee, tea, cola, energy-drinks, or other caffeinated beverages per day.
18. Is currently a regular or recreational user of cannabis, any illicit drugs or has a history of drug (including alcohol) abuse within approximately 3 months.
19. Has participated in a PET study or other study involving administration of a radioactive substance or ionizing radiation within 12 months prior to the screening visit, or has undergone an extensive radiological examination within this period with a radiation burden over 30 mSv (such as a CT-scan exam or a nuclear medical examination).
20. Suffers from claustrophobia or an inability to tolerate confinement in small places and would be unable to undergo MRI or PET scanning.
21. Is any concern by the investigator regarding (1) the safe participation of the subject in the trial, (2) the ability of the subject to tolerate procedures (for example, subjects with vague low back pain syndromes or subclinical hyperactivity spectrum disorders), or (3) for any other reason the investigator considers the subject inappropriate for participation in the trial.
22. Is or has an immediate family member (e.g., spouse, parent/legal guardian, sibling or child) who is investigational site or sponsor staff directly involved with this trial.

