Figure 2	Study Design Part II.....	14
Figure 3	Study Design Part III	15

SUMMARY OF CHANGES

PRIMARY REASON(S) FOR THIS AMENDMENT:

Section Number (s)	Section Title(s)	Description of Change (s)	Rationale
5.1.3	Subject Exclusion Criteria: Part III	Updated exclusion criterion # 19 regarding prior exposure to radiation to exclude subjects who underwent a radiological exam with a radiation burden exceeding 30 mSv (change from 10 mSv).	Updated eligibility criterion to align with the level of radiation burden associated with radiological exams typically conducted at the Part III trial site. This change was made to expand on the potential pool of study participants who are under the care of the Part III trial investigator.
6.1.3	Trial Flow Chart Part III	Removal of predose urine/blood drug screen and footnote "h" associated with this procedure	Removed non-critical study procedure to reduce unnecessary burden on Alzheimer's Disease (AD) study participants. Based on the nature of the study population, it is expected that any negative drug screen test results from the Screening Visit will not change prior to dosing for subjects already deemed eligible for the trial.

ADDITIONAL CHANGE(S) FOR THIS AMENDMENT:

Section Number (s)	Section Title (s)	Description of Change (s)	Rationale
4.2.2	Rationale for Dose Selection/ Regimen/Modification	Updated to include acceptable yearly limit (Effective Dose [ED] <50 mSv) for radiation exposure in the US.	Update to reflect acceptable annual limits for radiation dose in the geographic region where Part III is to be conducted.
6.1.3	Trial Flow Chart Part III	For footnotes “b” and “c” pertaining to the timing of vital signs and ECG measurements, the timing for end of scanning session is corrected to read “(~90 minutes post-dose)” instead of “(~2 hours post-dose)”.	Correction to align with PET scan duration (up to ~ 90 minutes) planned for Part III
7.1.4.3	Domiciling	Clarification that subjects in Part III of the study will report to the research center on Day 1 (whereas subjects in Part I of the study will report to the research center on Day -1)	Update to reflect operational logistics/study conduct at Part III trial site
7.1.5.1	Screening (Part I, Part II and Part III)	Clarified that screening can occur within the 4 week visit window.	Clarification on timing of screening procedures

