Part II of this study will begin the process of validating and qualifying [^{11}C]MK-6884 as a M4 PAM tracer in humans. Part II will only be initiated if there is no indication of radiochemical toxicity, undue radiation risk or medically meaningful effect on physiology observed during Part I based on review of the safety and radiation safety data. [^{11}C]MK-6884 doses administered in Part II may be adapted to insure that the maximum exposure remains below the yearly limit of 10 mSv and within the acceptable limits for healthy human volunteers (see Section 4.2.2, Rationale for Dose Selection). The possibility of reliably quantifying M4 receptor availability will be determined by measuring the intra-subject -TRT variability. Subjects will be administered 2 separate IV doses of [^{11}C]MK-6884 separated by sufficient time (at least 3 hours) to allow most of the radioactivity from the first administration to decay prior to administering the second dose. The 2 doses will be administered preferably on the same day in order to limit the number of arterial punctures to one per evaluation. An alternate day for the second dose may be scheduled in case of technical difficulties at the discretion of the investigator.

An MRI scan of the brain will be obtained for ROI delineation. Positron emission images will be acquired for up to 2.0 hours after the administration of [^{11}C]MK-6884. It is expected that 90 minutes will be sufficient to characterize the regional cerebral tracer kinetic curves. The scanning duration may be adjusted based on available data. In addition, a CT scan, to enable attenuation correction, will be performed either before or after the PET scan. Arterial blood sampling for quantification of total radioactivity and the relative [^{11}C]MK-6884 fraction in plasma will be performed to provide a measure of radioactive material available in the brain. Arterial input function methodology is invasive and a non-invasive approach is preferable. In order to perform future studies non-invasively, a reference region (region in the brain devoid of M4 receptor) is necessary and will be assessed in this study. Clinical and laboratory safety evaluations will also be performed following administration of each dose of [^{11}C]MK-6884.

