The preliminary measurement of the radiation absorbed dose from [¹¹C]MK-6884 to Standard Reference Man was estimated with data from these three nonhuman primates. Based on this, administration of one 370 MBq (10 mCi) dose or two 370 MBq (10 mCi) doses of [¹¹C]MK-6884 is predicted to result in a human Effective Dose (ED) of 1.9 mSv or 2.9 mSv, respectively (accounting for 1 WB CT resulting 0.5 mSv/scan in Part I and two head CTs resulting ~0.05 mSv/scan in Part II). Thus the radiation dose to human in the planned studies is predicted to be within acceptable yearly limits (ED < 10 mSv) for healthy subjects. This is thought to represent a dose that conforms to the As Low As Reasonably Achievable (ALARA) principle of radiation exposure. Based on pre-clinical studies this dose should provide the minimum image quality necessary to quantify tracer binding in the brain while minimizing tracer exposure for healthy subjects. This is well below the desired yearly limit of ED = 10 mSv.

[¹¹C]MK-6884 will always be administered in an open-label manner. For each scan, patients/subjects will be administered an anticipated IV dose of ≤ 4.9 µg of MK-6884 based on assumptions of a 6 mCi single injection of a tracer with minimum specific activity of 500 Ci/mmol, as explained in Section 4.2.2.1 - Maximum Doses/Exposure for This Trial. In general, cyclotron produced ¹¹C tracers have been offering specific activity much higher than

500 Ci/mmol. Therefore, the administration of 10 mCi dose of [¹¹C]MK-6884 is anticipated to result in a maximum mass dose below 4.9 µg. The actual doses that will be administered during all parts will be adjusted based on the specific activity not to exceed the maximum mass of 4.9 µg and maximum allowed radiation exposure of 10 mSv per year in Europe or 50 mSv per year in the United States.

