5.7.5 Other

For potential subjects in Parts II and III (which require a baseline MRI scan), X-rays may be acquired, if indicated, as part of the screening procedures to confirm absence of indwelling metal fragments.

Investigators and designees may conduct other evaluations as medically indicated should adverse events occur or unanticipated problems arise that could have an impact on the health or wellbeing of the research volunteers. Diagnostic evaluations and treatment interventions should be rendered according to the standard of local medical care in the country in which each site is located.

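### Exclusion criteria 14 (Part I), 17 (Part II) and 19 (Part III) test prior clinical radiation one examination at a time and never sum it; in Parts I and II the cut-off also equals the 10 mSv yearly limit

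*Combined protocol and SAP*

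**What the plan says.** Each of the three criteria in Section 5.1.3 has two limbs.

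- **Research exposure.** A subject is excluded who "Has participated in a PET study or other study involving administration of a radioactive substance or ionizing radiation within 12 months" before screening. There is no dose threshold.
- **Clinical imaging.** In Parts I and II a subject is excluded who "has undergone an extensive radiological examination within this period with a radiation burden over 10 mSv". In Part III the text is "has undergone an extensive radiological examination within this period with a radiation burden over 30 mSv". The wording is singular, and no rule covers several examinations.

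Section 4.2.2 gives the limits by region: a "maximum allowed radiation exposure of 10 mSv per year in Europe or 50 mSv per year in the United States". The 10 mSv figure is applied to healthy subjects in 4.2.2 and to Part II in 4.2.1, where doses may be adapted so that "the maximum exposure remains below the yearly limit of 10 mSv". The Summary of Changes places Part III under the US figure; the reason given is "Update to reflect acceptable annual limits for radiation dose in the geographic region where Part III is to be conducted".

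Section 4.2.2 predicts 1.9 mSv for one dose with a whole-body CT (Part I) and 2.9 mSv for two doses with two head CTs (Part II). Section 7.1.5.5 allows up to two repeat scans per subject and upward adaptation of the radiation dose, provided the yearly limit is kept. Section 7.2.1 tolerates up to 10% more activity than prescribed. Section 5.7.5 adds that in Parts II and III "X-rays may be acquired, if indicated, as part of the screening procedures to confirm absence of indwelling metal fragments"; the 2.9 mSv estimate does not include these.

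**The concern.** A per-examination test ranks subjects wrongly. In Parts I and II one 11 mSv examination excludes, while two 9 mSv examinations, 18 mSv in all, do not. This holds however the yearly limit is read.

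The second issue is specific to Parts I and II, where the screening cut-off and the yearly limit are the same number. If the limit is meant to include what a subject received before the trial, a subject just under the cut-off has almost no room left for the study dose. Sections 4.2.2 and 7.1.5.5 would still forbid exceeding the limit, but no listed procedure produces the prior-dose total needed to apply that rule to a given person.

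These are healthy volunteers, who can generally expect no direct benefit. On the inclusive reading, an affected subject would exceed the limit, receive a reduced dose, or lose a scan. In Part II a lost retest removes one test-retest pair from a planned 6 to 10, unless the subject is replaced.

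**Working it through.** **Inputs**

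- Effective dose coefficient: 0.0038 ± 0.0002 mSv/MBq, from three rhesus monkeys (4.2.2).
- Activity: 370 MBq per injection; one injection in Parts I and III, two in Part II (5.2, Table 2).
- CT: 0.5 mSv whole-body in Part I, about 0.05 mSv per head CT in Part II (4.2.2). No figure is given for Part III; I assume one head CT at 0.05 mSv.
- Tolerance: +10% activity (7.2.1). Repeats: up to two (7.1.5.5); I assume each has its own CT.
- The 9 and 25 mSv examinations are illustrative assumptions.

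**1. The plan's own figures**

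Per injection: 370 × 0.0038 = 1.406 mSv.

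- Part I: 1.406 + 0.5 = 1.906, stated as 1.9.
- Part II: 2 × 1.406 + 2 × 0.05 = 2.912, stated as 2.9.
- Part III: 1.406 + 0.05 = 1.456.

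Both stated figures reproduce.

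**2. If the limit counts trial dose only**

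With +10%, one injection gives 1.1 × 1.406 = 1.5466 mSv. With two repeats:

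- Part I: 3 × (1.5466 + 0.5) = 6.140 mSv.
- Part II: 4 × (1.5466 + 0.05) = 6.386 mSv.

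Both are below 10 mSv.

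**3. Effect of not summing**

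- Parts I and II, two assumed 9 mSv examinations: 18 + 1.906 = 19.9 mSv and 18 + 2.912 = 20.9 mSv. Both subjects pass screening.
- Part III, two assumed 25 mSv examinations: 50 + 1.456 = 51.5 mSv, beside a limit of 50. The subject passes.
- Part III, one examination at the cut-off: 30 + 1.456 = 31.5 mSv. The gap to 50 therefore holds only for a single examination.

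**4. If the limit counts prior exposure (Parts I and II)**

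Room for prior burden = 10 − planned dose.

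| | Planned dose | Room | Total for a subject at the 10 mSv cut-off |
|---|---|---|---|
| Part I | 1.906 | 8.094 | 11.906 |
| Part II | 2.912 | 7.088 | 12.912 |

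A prior burden above about 8.1 or 7.1 mSv passes screening but does not leave room for the planned dose.

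**5. Cut-offs that allow for the 10% tolerance**

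- Part I: 10 − (1.5466 + 0.5) = 7.953. Rounded down to 7.9, the total is 7.9 + 2.047 = 9.947.
- Part II: 10 − (2 × 1.5466 + 0.1) = 6.807. Rounded down to 6.8, the total is 6.8 + 3.193 = 9.993.

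Over 0.0036 to 0.0040 mSv/MBq the room runs from 8.035 down to 7.872 (Part I) and from 6.970 down to 6.644 (Part II). At the upper coefficient 7.9 and 6.8 no longer suffice: 7.9 + 2.128 = 10.03 and 6.8 + 3.356 = 10.16. They are provisional until human dosimetry exists.

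**6. Room if scans are repeated (+10%, with CT)**

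- Part I: one repeat 10 − 4.093 = 5.9 mSv; two repeats 10 − 6.140 = 3.9 mSv.
- Part II: one repeat 10 − 4.790 = 5.2 mSv; two repeats 10 − 6.386 = 3.6 mSv.
- Part III with 30 mSv applied to the sum and two repeats: 30 + 3 × 1.5966 = 34.8 mSv, well below 50.

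**The case against.** The strongest reply is that the yearly limit governs trial dose alone. Section 4.2.2 compares it only with trial dose ("the radiation dose to human in the planned studies is predicted to be within acceptable yearly limits"), and Sections 2.1, 4.2.1 and 7.1.5.5 mention it when they restrict tracer doses. No section says that clinical imaging counts. The imaging limb can still serve an ordinary purpose: not adding research radiation soon after a high-dose examination. Two values that both equal 10 need not have been meant to be added. All of this stands, so the headroom argument is conditional.

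Existing safeguards also count. Section 7.1.5.5 makes repeat decisions subject by subject and requires the sponsor and investigator to accept the added exposure. The investigator-concern criteria (Part I no. 16, Part II no. 19, Part III no. 21) allow exclusion on safety grounds. These soften the problem, but none calls for a total or gives a number.

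A reader might infer three stronger points that the documents do not support:

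- *That the plan permits a breach of the yearly limit.* On the trial-dose-only reading nothing is exceeded. On the inclusive reading, going over would violate 4.2.2 and 7.1.5.5.
- *That Part III's 30 mSv against 50 mSv shows headroom was intended there and forgotten in Parts I and II.* The Summary of Changes explains 30 mSv by the examinations usual at the Part III site and by recruitment. Criterion 19 is also per examination.
- *That a lost retest necessarily costs a pair.* Section 5.9 allows replacement of a subject who discontinues.

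**Conclusion.** The concern holds as a gap in the screening rule. In all three Parts, several examinations below the cut-off pass whatever their total; this follows from the wording alone.

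The lack of headroom in Parts I and II depends on the 10 mSv limit counting prior clinical exposure, which the documents leave open. If it does, the affected subjects are those with a prior burden above about 8.1 mSv (Part I) or 7.1 mSv (Part II). If it does not, the largest trial dose is about 6.4 mSv and the limit is kept. The Part III total of 51.5 mSv matters against the 50 mSv limit on the same condition.

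The figures rest on the rhesus-based coefficient and the CT doses in 4.2.2. The documents do not show how many volunteers would have such imaging; it is probably few. This is a cheap improvement to subject protection, and it is useful on either reading because a sum is a better measure of prior burden than the largest single examination.

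**What to change.** 1. **Criteria 14, 17 and 19:** replace the single-examination test with the summed radiological burden over the prior 12 months, counted back from dosing so that any screening X-ray under 5.7.5 is included.
2. **Parts I and II:** require that this sum plus the planned study dose, at the current dosimetry estimate and with the 10% activity tolerance, stays below 10 mSv. At the rhesus-based estimate this allows a prior burden of up to about 7.9 mSv (Part I) or 6.8 mSv (Part II). Update both when Part I dosimetry is available.
3. **Part III:** keep 30 mSv, applied to the sum.
4. **Section 7.1.5.5:** check the same running total before any repeat scan or upward dose adaptation.
5. **Section 4.2.2:** state that the yearly limit is applied in this way, prior clinical exposure included.

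The cost is wording in three criteria, a sentence each in 4.2.2 and 7.1.5.5, and one sum per subject. A few volunteers with recent high-dose imaging become ineligible.
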